Work by Patchell et al. demonstrated that whole brain radiotherapy (WBRT) after surgical resection of a single brain metastasis reduced the rate of recurrence at the site of the original metastasis and at other sites of the brain.³ It also decreased the likelihood of death from neurologic causes. However, WBRT is not without side effects; there is particular concern with the long-term neurocognitive effects of treatment.

As a result, postoperative stereotactic radiosurgery (SRS) and less than 5 fractions of stereotactic radiation therapy (SRT) has become increasingly popular. SRS/SRT delivers high doses of radiotherapy via multiple beam angles and highly conformal planning techniques to the target, sparing normal brain tissue. A randomized trial by Brown et al. found that postoperative SRS had similar overall survival (OS) when compared to postoperative WBRT (median OS of 12.2 months vs. 11.6 months, respectively [p = 0.70]) but had lower rates of cognitive deterioration (52% vs 85% [p<0.001]).⁴ When compared to observation after surgery, a separate trial demonstrated improved local control with postoperative SRS.⁵

There is growing interest in whether SRS/SRT delivery for brain metastases can be transitioned to the preoperative (or neoadjuvant) setting. Radiotherapy has been used neoadjuvantly for many disease sites, including rectal, pancreatic, esophageal and sarcomatous cancers. Neoadjuvant timing for brain metastases offers several potential benefits. First, target delineation is much simpler preoperatively compared to postoperatively (where the tumor bed is large and can change over time). This smaller treatment volume may also decrease the risk of toxicity or radiation necrosis.

Neoadjuvant radiotherapy may also help with disease control. Local recurrence remain somewhat high (~44%) for tumors greater than 3cm in diameter,⁵ likely related to tumor spill at the time of surgery. In addition, there is concern for leptomeningeal spread after surgery due to surgical tract seeding into the meningeal space. Preoperative SRS or SRT to the tumor may serve as a way to, in effect, "sterilize" the tumor site and reduce the risk of local recurrence and leptomeningeal spread. Series have suggested that neoadjuvant SRS or SRT results in lower rates of leptomeningeal disease when compared to postoperative SRS or SRT.

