The purpose of this study is to prospectively compare preoperative (neoadjuvant) SRS/SRT to postoperative (adjuvant) SRS/SRT in patients undergoing surgical resection for brain metastases.

Hypothesis, Objectives, and Outcomes

We hypothesize that neoadjuvant SRS/SRT prior to surgical resection of brain metastases will result in improved freedom from Central Nervous System (CNS) events when compared to adjuvant SRS/SRT after surgical resection.

Primary Objectives

- Our primary objectives are: (1) to determine the *Time to a Central Nervous System* (*CNS*) *Composite Event* (*CE*) in subjects who receive either neoadjuvant (preoperative) SRS/SRT or adjuvant (post-operative) SRS/SRT for their brain metastases, and (2) to compare the two treatment arms for evidence of improved Time to a CNS CE among subjects who received neoadjuvant SRS/SRT.
 - A CNS CE will consist of one of the following three events: Local Recurrence (LR) of the treated lesions, symptomatic radiation necrosis (SRN) to the treated lesions, or development of leptomeningeal disease (LMD). See below for detailed definitions of LR, SRN, and LMD.
 - Time to a CNS CE, the primary outcome, will be measured as the time from the date of randomization to the date of a documented LR, SRN, or LMD, whichever occurs first.
 - Death before occurrence of a CNS CE will be treated as a competing risk. Study participants who are alive and have yet to experience a CNS CE at their last evaluation will be right-censored for Time to CNS CE on the date of their last evaluation.

Secondary Objectives related to the Primary Objective. Some of our secondary objectives include (a) determining in each study subject the *secondary outcomes* listed below, and (b) comparing the treatment arms for evidence of improvements in these secondary outcomes.

- Index lesion local recurrence (ILLR), a component of CNS CE, will be defined as the development of new nodular contrast enhancement in the surgical bed compared with the immediate postoperative MRI.
- Non-index lesion LR, also a component of CNS CE, will be defined as an increase of more than 25% in the size of any treated non-resected brain lesion.

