Other Secondary Objectives include determining the other secondary outcomes described below, and comparing treatment arms for improvements with neoadjuvant SRS/SRT in (a) the rates of secondary yes/no outcomes such as Local Control, or (b) the 6-month, 12-month, 18-month, month rates of secondary time-to-event outcomes such as Duration of Local Control:

- Local Control.
 - Local Control will be defined as Complete Response [CR], Partial Response [PR], or Stable Disease [SD] of the index lesion resulting from the assigned treatment. It will be determined at the first evaluation following successful completion of either neoadjuvant or adjuvant SRS/SRT of all metastatic lesions and surgical resection of the index lesion.
 - Stratified by GTR or STR, piecemeal vs en bloc resection

- Treatment Failure will be defined either as Progressive Disease [PD] during the assigned treatment, or as the absence of Local Control at the first evaluation following successful completion of the assigned treatment.
- Duration of Local Control (DLC) will be measured as the time from the date when Local Control is first documented to the date when:
 - the treated lesions show documented evidence of LR or PD, or
 - the patient undergoes whole-brain radiotherapy, repeat SRS, repeat surgical intervention
- Time to distant in-brain failure.
 - Distant in-brain failure (DiBF) will be defined as the occurrence of any new parenchymal lesion outside of the planning target volume.
 - Time to DiBF will be measured as the time from the date of randomization to the date of occurrence of the DiBF. Death before occurrence of DiBF will be treated as a competing risk. Study subjects who are alive and free of DiBF at their last evaluation will be right-censored for Time to DiBF on the date of their last evaluation.
- Overall survival.
 - Overall survival (OS) will be measured as the time from the randomization date to the date of death for any reason. Study participants who are still alive at last follow-up will be right-censored for OS on the date of their last follow-up.
- Time to systemic therapy.
 - Time to initiation or re-initiation of systemic therapy will be measured as the time from the date when the assigned treatment (neoadjuvant versus adjuvant SRS/SRT) is successfully completed to the date when the systemic therapy is initiated or re-initiated.

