- Time to subsequent brain treatment, including whole-brain radiotherapy (WBRT), will be measured as the time from the date when the assigned treatment is successfully completed to the date when the WBRT or other subsequent treatment is initiated.
- Radiation/Surgery toxicity
 - o The rate of symptomatic (≥grade 2) radiation/surgery toxicity

 Incidence of adverse events as graded by the National Cancer Institute (NCI) Common Terminology Criteria for Adverse Events (CTCAE) version 5.0

Study Design and Procedures

Design: This pilot study is a randomized, open-label, 2-arm active-controlled phase II clinical trial conducted at a single study site (UAMS) located in central Arkansas. Prospective enrollees will be screened based on the inclusion/exclusion criteria listed below in the *Study Population* section. Study-eligible candidates who agree to participate will be assigned by randomization to one of the 2 treatment arms shown in the table below:

Treatment Arm	Intervention/treatment
Experimental: Arm I (pre-operative SRS/SRT)	Radiation: Stereotactic Radiosurgery Undergo SRS/SRT Other Names:
Patients undergo SRS or SRT within 15 days of randomization followed by surgery within 15 days of radiation completion. Patients may undergo	Stereotactic External Beam Irradiation
	 stereotactic external-beam radiation therapy
additional SRS or SRT if disease returns after treatment.	stereotactic radiation therapy
	Stereotactic Radiotherapy
	 stereotaxic radiation therapy
	 stereotaxic radiosurgery
Active Comparator: Arm II (post- operative SRS/SRT) Patients undergo surgery within 15 days of randomization followed by standard-of-care SRS or SRT within 30	Undergo SRS/SRT Other Names: • Stereotactic External Beam Irradiation
	 stereotactic external-beam radiation therapy
days of surgery. Patients may undergo additional SRS or SRT if disease	stereotactic radiation therapy
returns after treatment.	Stereotactic Radiotherapy
	 stereotaxic radiation therapy
	stereotaxic radiosurgery

The dose, volume and fractionation of radiotherapy will be at the discretion of the radiation oncologist at the time of SRS/SRT depending on the size, location, and proximity to critical structures. Before treatment commences, each study participant will be stratified according to two stratification factors:

- Size of Index Lesion (<3 cm versus ≥3 cm)
- Number of Brain Metastases (4 or fewer versus 5 or more)

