A potential benefit to study participants is the potential improved target delineation with neoadjuvant SRS/SRT. Since the tumor bed can change over time, adjuvant SRS/SRT involves challenges in delineating the target volume of a dynamically changing target, which may lead to geographic miss and increased radiation dose to normal tissues. Improved target delineation with neoadjuvant SRS/SRT may potentially improve local control and reduce toxicity.

A potential benefit to study participants is a potential reduction in the rates of radiation necrosis. With neoadjuvant SRS/SRT, the tumor and adjacent normal tissue that has been irradiated is removed at the time of surgery, reducing the availability of injured tissue and inflammatory reaction needed to precipitate radiation necrosis. In contrast, for adjuvant SRS/SRT, the irradiated tissue remains. Retrospective data suggests the rate of symptomatic radiation necrosis is lower with neoadjuvant SRS/SRT compared to adjuvant SRS/SRT.⁶

A potential benefit to study participants is a potential reduction in the rates of leptomeningeal disease. With neoadjuvant SRS/SRT, the tumor site is "sterilized" and the risk of leptomeningeal disease may be minimized even with tumor spill, as tumor cells may be replicatively dead. Retrospective data suggests the rate of symptomatic radiation necrosis is lower with neoadjuvant SRS/SRT compared to adjuvant SRS/SRT.⁶

A potential benefit to study participants is potential immune system activation against tumor cells. Radiotherapy to an intact tumor may allow for increased immune activation and in situ vaccination, allowing for greater immune response against the tumor cells. Animal models have suggested this benefit but it is not well-studied in human subjects.⁸

Finally, knowledge gained from the study could potentially benefit patients in the future.

Data Handling and Recordkeeping

The Principal Investigators will carefully monitor study procedures to protect the safety of research subjects, the quality of the data and the integrity of the study.

Information will be coded with the key to the code kept separately. Data will be stored securely on UAMS-maintained computers and servers. Only investigators listed on this protocol will have direct access to patient-identifying data. Research assistants, coordinators, and statisticians will only have access to coded data. At the conclusion of the study, the coded data will be de-identified.

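### Distant in-brain failure is bounded by the planning target volume, which for the index lesion is set by the randomized timing, so one surgical-bed nodule can count as distant failure in Arm I only

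*Combined protocol and SAP*

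**What the plan says.** The definition, under Other Secondary Objectives, reads: "Distant in-brain failure (DiBF) will be defined as the occurrence of any new parenchymal lesion outside of the planning target volume". Time to DiBF runs from randomization, with death as the competing risk. The Statistical analysis plan lists DiBF among the events to be compared between arms with a Fine and Gray model, one-sided for improvement on the pre-operative arm at alpha 0.10.

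The treatment-arm table in Study Design and Procedures fixes when the volume is drawn. Arm I: "Patients undergo SRS or SRT within 15 days of randomization followed by surgery within 15 days of radiation completion". Arm II: "Patients undergo surgery within 15 days of randomization followed by standard-of-care SRS or SRT within 30" days of surgery. The same section gives no margin and states: "The dose, volume and fractionation of radiotherapy will be at the discretion of the radiation oncologist".

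The background says that "target delineation is much simpler preoperatively compared to postoperatively (where the tumor bed is large and can change over time"), and adds: "This smaller treatment volume may also decrease the risk of toxicity or radiation necrosis". Potential benefits repeats the point: "adjuvant SRS/SRT involves challenges in delineating the target volume of a dynamically changing target".

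Index-lesion LR, a component of the primary composite, has a different boundary. It is "new nodular contrast enhancement in the surgical bed", judged against the immediate postoperative MRI.

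**The concern.** The boundary of an outcome should not depend on the treatment being compared. Here it does. The planning target volume for the index lesion is part of the randomized intervention, and the protocol itself expects it to be smaller when radiation comes first. Two patients with the same nodule at the same place in the resection bed can be classified differently on DiBF solely because of their arm.

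At stake is a secondary comparison that the plan formally tests and summarises at 6, 12 and 18 months. An excess of DiBF in Arm I could appear without any difference in disease, or a real reduction could be hidden.

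**Working it through.** The plan gives no DiBF rate, margin or DiBF power, so there is no figure to reproduce. The check is a comparison of definitions, followed by an illustration on assumed rates.

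**Step 1: apply the two definitions as written to a new parenchymal nodule near the resected index lesion.**

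| Site of nodule | Index-lesion LR | DiBF |
|---|---|---|
| In the bed, inside the planning target volume | yes | no |
| In the bed, outside the planning target volume | yes | yes |
| Outside the bed, inside the planning target volume | no | no |
| Outside the bed, outside the planning target volume | no | yes |

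The LR column depends only on the bed, which is read on the postoperative MRI in both arms. The DiBF column depends only on the planning target volume. Radiation precedes surgery in Arm I, so the volume surrounds intact tumour; it follows surgery in Arm II, so the volume surrounds the bed. If the Arm I volume is the smaller, as the background says, bed nodules fall in the second row more often in Arm I and in the first row more often in Arm II. LR is the same in both rows; DiBF is not.

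**Step 2: look for text that repairs this.** No sentence makes LR and DiBF mutually exclusive, removes the surgical bed from DiBF, or sets a reference common to both arms.

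**Step 3: illustrate the possible size.** Inputs:
- Death hazard d = 0.32 per year in both arms: the 32% per year in the sample-size section, used as a hazard.
- True distant hazard h = 0.30 or 0.50 per year, equal in both arms: assumed.
- Rate m of bed-edge nodules outside the Arm I volume but inside the Arm II volume = 0.02, 0.05 or 0.10 per year: assumed. These add to DiBF in Arm I only.

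Formulas, with constant hazards:
- Apparent cause-specific hazard ratio, Arm I to Arm II = (h + m) / h.
- Cumulative incidence at t years = H / (H + d) × (1 − exp(−(H + d)t)), with H = h + m in Arm I and H = h in Arm II.

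Worked case, h = 0.30, m = 0.05, t = 1: the ratio is 0.35 / 0.30 = 1.17. Arm I: 0.35 / 0.67 × (1 − exp(−0.67)) = 25.5%. Arm II: 0.30 / 0.62 × (1 − exp(−0.62)) = 22.4%.

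| h | m | Apparent ratio | 12-month DiBF, Arm I | 12-month DiBF, Arm II |
|---|---|---|---|---|
| 0.30 | 0.02 | 1.07 | 23.6% | 22.4% |
| 0.30 | 0.05 | 1.17 | 25.5% | 22.4% |
| 0.30 | 0.10 | 1.33 | 28.5% | 22.4% |
| 0.50 | 0.02 | 1.04 | 35.2% | 34.1% |
| 0.50 | 0.05 | 1.10 | 36.7% | 34.1% |
| 0.50 | 0.10 | 1.20 | 39.2% | 34.1% |

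Masking follows from the same arithmetic. With m = 0.05, a true distant hazard of 0.25 in Arm I against 0.30 in Arm II (0.25 / 0.30 = 0.83) would be observed as 0.25 + 0.05 = 0.30 against 0.30, a ratio of 1.00.

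These are cause-specific ratios; the Fine and Gray ratio would not be identical. They show direction and plausible scale, not an estimate for this trial.

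**The case against.** **Wording.** The LR definition speaks of enhancement in the bed, while DiBF speaks of a new parenchymal lesion and is labelled distant. A sensible reader might treat bed recurrence as already assigned to LR. That is plausible, but the protocol does not say so, its LR definition also calls bed recurrence new, and the only stated test for DiBF is position relative to the planning target volume.

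**Direction.** The extra events fall in Arm I, while the test looks only for improvement in Arm I. A false claim of benefit on DiBF becomes less likely. This stands, and it limits the harm to a masked benefit or an apparent excess.

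**Primary endpoint.** A reader might infer that a marginal Arm I recurrence could be relabelled distant and so drop out of the primary composite, favouring Arm I. The documents do not support this. LR is bed-based in both arms, so a bed nodule remains LR, and a composite event, even if it also meets the DiBF definition. Losing it would require a reader to disregard the LR definition. Open-label reading is a separate matter that would arise under any DiBF boundary.

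**Size.** A reader might try to size the effect by geometry. With an assumed 2 mm margin, a 3 cm tumour gives a sphere of diameter 3.4 cm, π/6 × 3.4³ = 20.6 cm³; postoperative targets of 3.5 and 4 cm give diameters of 3.9 and 4.4 cm, or 31.1 and 44.6 cm³. The differences of 10.5 and 24.0 cm³ are not peri-cavity brain, because much of each sphere may be cavity. If the assumed target is the cavity itself, the rim of tissue is only 8.6 or 11.1 cm³. The documents give none of these dimensions, and volume is not event frequency.

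**Conclusion.** The point holds as an arm-dependent boundary in one secondary outcome. Applied literally, the definition counts a bed nodule outside the Arm I volume as both LR and DiBF, and the same nodule inside the Arm II volume as LR only. The likely bias is against the pre-operative arm.

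This rests on the protocol's own statement that the preoperative volume is smaller, and on the definitions being applied as written. Because volume is discretionary and no margin is stated, neither the size of the bias nor its direction in an individual patient can be determined. The ratios of 1.04 to 1.33 depend wholly on the assumed rates. The primary composite and its power calculation are not affected if the LR definition is followed. The point merits correction because the comparison is formally tested and the remedy is cheap.

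**What to change.** In the DiBF definition under Other Secondary Objectives:

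- For the index lesion, replace the planning-target-volume boundary, in both arms, with the surgical bed on the immediate postoperative MRI, the reference that index-lesion LR already uses.
- State that a new nodule in the bed is LR and not DiBF, wherever the planning target volume lay.
- Keep the planning-target-volume boundary for non-index lesions, which are treated unresected in both arms.
- Record each event's position relative to the planning target volume as a descriptive item.

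Two broader changes are best avoided. Counting a nodule along the surgical tract as LR would widen a component of the primary composite. Requiring a fixed distance from every treated lesion would leave a gap: a new nodule beside a non-index lesion would not be DiBF, and might not be LR either, since that requires growth of more than 25% in the treated lesion.

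The cost is endpoint wording and one event-form field, with no new imaging. The small downside is that in-field versus out-of-field failure at the index site becomes descriptive only. The extent of the bed remains a reading judgement, but with the same reference in both arms. The change should be made before events are classified.

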- Patients with prior histopathological diagnosis of cancer other than small cell lung cancer, lymphoma, and germ cell histologies.
- MR imaging of the brain with findings strongly suggestive of metastatic tumor(s) as assessed by the radiologist.
- Seen by a neurosurgeon or radiation oncologist and judged to be appropriate for participation in this study, including the ability to tolerate both surgery and SRS/SRT, e.g., the ability to lie flat in a stereotactic soft head frame.
- ECOG ≤ 2
- 1-2 index lesion(s) appropriate for resection, not previously treated with SRS/SRT. Index lesion(s) should be ≥ 1.5 cm and < 5 cm in largest dimension, and require resection. Alternatively, patients with a diagnosis of melanoma and a lesion < 1.5cm in largest dimension may also be included.
 - All other brain lesions must be appropriate for SRS/SRT alone and treated according to physician preference. Prior neurosurgery and/or prior SRS/SRT at a non-overlapping location are permitted at the discretion of the treating physician.
- MRI confirmed 1-10 lesions, 1-2 of which are the index lesions undergoing surgery. Each non-index lesion (up to 10) must measure ≤ 3.0 cm in maximal extent on contrasted MRI scan, and not otherwise require resection.
- Clinical indication and plan for stereotactic radiosurgery to all known brain lesions requiring treatment (≤ 10 metastases).
- Surgical resection able to be performed within 15 days of radiotherapy completion.
- Written informed consent obtained from subject, or a legally designated power of attorney and ability for subject to comply with the requirements of the study.
- Negative pregnancy test in women of childbearing potential (WOCBP) within 30 days of radiation. WOCBP is a female patient less than 50 years of age or who has menstruated within the last 12 months.
- Platelet count > 80 k/cumm, Hgb > 7.5 gm/dL, INR < 1.3, ANC > 1.5 k/cumm

Exclusion Criteria

- Not a surgical candidate per neurosurgeon's discretion.
- Contraindication to general anesthesia.
- Not a radiosurgical candidate per radiation oncologist's discretion.
- Metastatic germ cell tumor, small cell carcinoma, leukemia, multiple myeloma or lymphoma or any primary brain tumor
- ECOG > 2
- < 3 months expected survival
- Radiologic documentation of hydrocephalus in addition to symptoms of hydrocephalus
- Radiographic or cytologic evidence of leptomeningeal disease.
- Imaging Findings:

- Midline shift > 6mm
- \circ >10 lesions, one of which is the index lesion

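### Distant in-brain failure is timed from randomization but defined against a target volume set by day 15 in Arm I and as late as day 45 in Arm II, so the same early lesion can count in one arm and not the other

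*Combined protocol and SAP*

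**What the plan says.** **DiBF.** Under Other Secondary Objectives, the event is the "occurrence of any new parenchymal lesion outside of the planning target volume". The clock is set in the same place: "Time to DiBF will be measured as the time from the date of randomization to the date of occurrence of the DiBF". The Statistical analysis plan lists DiBF among the outcomes compared by a Fine and Gray model, one-sided at the 10% level.

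**Timing.** The treatment-arm table under Study Design and Procedures gives, for Arm I: "Patients undergo SRS or SRT within 15 days of randomization followed by surgery within 15 days of radiation completion". For Arm II: "Patients undergo surgery within 15 days of randomization followed by standard-of-care SRS or SRT within 30", continuing in the broken table cell "days of surgery. Patients may undergo additional SRS or SRT if disease" (the sentence goes on to recurrence after treatment, and Arm I has the same allowance).

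**Target.** Below the table: "The dose, volume and fractionation of radiotherapy will be at the discretion of the radiation oncologist at the time of SRS/SRT".

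**Lesions treated.** The inclusion criteria require: "Clinical indication and plan for stereotactic radiosurgery to all known brain lesions requiring treatment", to a maximum of 10. The Local Control definition also takes the assigned SRS/SRT to cover all metastatic lesions.

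**Primary composite.** Local recurrence and symptomatic radiation necrosis refer to the treated lesions. Non-index recurrence is an increase "of more than 25% in the size of any treated non-resected brain lesion".

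No endpoint definition refers to the eligibility MRI, and nothing says how to classify a lesion first seen between randomization and SRS/SRT.

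**The concern.** The DiBF clock starts before a target volume need exist in either arm, and the volume that decides what counts is set at a time that depends on the assigned arm. New lesions in the early weeks can therefore be sorted differently by arm with no difference in biology.

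The planned comparison looks for improvement on the pre-operative arm. Early lesions counted in Arm I and absorbed into the target in Arm II would raise the Arm I cumulative incidence relative to Arm II, and the distortion falls early, so it matters most at the 6-month summary. There is also a possible knock-on effect on the primary outcome, because a lesion absorbed into the Arm II target becomes a treated lesion whose later growth or symptomatic necrosis can count.

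**Working it through.** **Tracing one lesion.** The index-lesion recurrence definition uses the immediate postoperative MRI as its reference, so that scan gives a route to detection within the protocol.

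- Arm I: SRS/SRT by day 15, then surgery, then the postoperative MRI. A new remote lesion on that scan lies outside a volume already drawn and is a DiBF.
- Arm II: surgery by day 15, then the postoperative MRI, then SRS/SRT up to 30 days after surgery. The same lesion can be included in the target, and it is then not outside the planning target volume.

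**Inputs from the documents.** Latest SRS/SRT is day 15 in Arm I and day 15 + 30 = 45 in Arm II, a difference of 30 days. There are 52 patients per arm, with 17.4 primary events projected in Arm II (Sample size, power, and study duration). The plan states no DiBF rate or DiBF power, so there is no figure of its own to reproduce here.

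**Assumptions.** The annual probability p of a new remote lesion is 20%, 40% or 60%, at a constant hazard; death is ignored; each lesion is detected at onset; and each lesion present before planning is put in the target.

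**Formula.** h = −ln(1 − p); P(d) = 1 − exp(−h × d / 365.25).

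| p per year | h | P(15) | P(45) | Difference | × 52 |
|---|---|---|---|---|---|
| 20% | 0.223 | 0.9% | 2.7% | 1.8 points | 0.9 |
| 40% | 0.511 | 2.1% | 6.1% | 4.0 points | 2.1 |
| 60% | 0.916 | 3.7% | 10.7% | 7.0 points | 3.6 |

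The difference is between the two outer limits. Earlier SRS/SRT in Arm II shrinks it. Earlier SRS/SRT in Arm I alone would widen it, with P(45) × 52 = 1.4, 3.2 or 5.6 patients as the ceiling.

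**Share of early DiBF.** By 6 months (182.6 days), P is 10.6%, 22.5% or 36.8%. P(45)/P(182.6) is 26% to 29%, and P(15)/P(182.6) is 9% to 10%. At the latest dates, up to those shares of first new lesions by 6 months could be absorbed into the target in Arm II and Arm I respectively.

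**Primary composite.** Suppose 10% to 50% of the affected lesions later cause recurrence or symptomatic necrosis (a second assumption), and no counterpart is counted in Arm I. The added Arm II events then run from 0.9 × 0.10 = 0.1 to 3.6 × 0.50 = 1.8, against 17.4 projected.

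**The case against.** **The lesion set is not expressly fixed at planning.** That it is fixed then is inferred from the DiBF definition and from the volume being decided at SRS/SRT. The inclusion criterion on known lesions is checked before randomization, where known naturally means known at entry, and lesion number is a stratification factor. A lesion seen before any target is drawn could also be called new and outside any volume on the day it appeared. This stands as far as it goes: the text permits an Arm II lesion to escape DiBF but does not compel it. Still, the documents nowhere freeze the list at entry, and a rule readable both ways in an open-label trial needs settling.

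**The full 30-day gap needs a late scan.** The only peri-treatment scan mentioned is the immediate postoperative MRI, and scheduled MRI begins after both treatments are complete. If Arm II targets are drawn from the postoperative scan, the lesion set closes near day 15 and most of the gap disappears. This stands, and it limits the size.

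**Absorbed does not mean lost.** An Arm II patient whose early lesion is treated stays at risk and can have a later DiBF, so some events are delayed, not removed. This also stands.

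**The primary outcome.** A reader might infer that these lesions enter the composite in Arm II only, so that the primary comparison is biased toward the hypothesis. The documents do not support that. The non-index recurrence wording covers any treated non-resected lesion without limiting it to the first course, and additional SRS/SRT is allowed in both arms. An Arm I lesion treated that way could be both a DiBF and a treated lesion.

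**Conclusion.** The point holds for DiBF. The definition depends on an arm-specific date, and under the stated rule the same early lesion can be a DiBF in Arm I and a planned target in Arm II. The bias runs against the pre-operative arm.

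The size is modest: about 1 to 4 of 52 patients for assumed rates of 20% to 60% per year, with both arms at their latest permitted dates, every lesion detected at once and every one included in the target. The 26% to 29% share of 6-month events is a worst case on the same assumptions and is not an expected loss.

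For the primary composite, the most that can be said is that the route differs. Such a lesion becomes treated in Arm II through the assigned course, but in Arm I only if additional SRS/SRT is given and counted. The resulting effect is small, conditional and of unsettled size, and a claim of established bias in the primary comparison would go too far.

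**What to change.** **DiBF.** Define it in both arms as any parenchymal lesion not present on the pre-randomization eligibility MRI and outside the index surgical site, dated to the first scan that shows it, whether or not it is later included in an SRS/SRT target.

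**Primary composite.** State one lesion-set rule and apply it to both arms, saying whether lesions first treated after randomization, in the assigned course or later, can contribute non-index recurrence or symptomatic necrosis. Which rule to adopt is an estimand choice for the sponsor; removing from the main analysis lesions that received the assigned SRS/SRT is debatable and is not needed here. Add a sensitivity analysis of the CNS composite in which non-index recurrence and symptomatic necrosis are restricted to lesions on the baseline MRI.

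**Cost.** This is a change of wording plus one extra analysis. The eligibility MRI is already required, no scan is added and no treatment changes. The downside is that scans before SRS/SRT in Arm II may date a few DiBF events early. A late planning scan there would act as an additional look, so the detection imbalance is reduced but may not vanish.
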